Safety profile of a novel vaccine not yet fully characterized.	Data available from Study C4591001 showed low incidence of severe or serious events, and no clinically concerning safety observations. The vaccine appears to be safe and well tolerated across the safety population and within demographic subgroups based on age, sex, race/ethnicity, country, and baseline SARS-CoV-2 status.	 Eligibility criteria have been selected to ensure that only appropriate participants are included in the study (see Section 5). AE and SAE reports will be collected from signing of the ICD through approximately 1 month after vaccination. All participants will be observed for 30 minutes after vaccination. 	
Potential for COVID-19 enhancement.	Disease enhancement has been seen following vaccination with RSV, feline coronavirus, and Dengue virus vaccines. No evidence of disease enhancement has been seen in a large-scale clinical study of BNT162b2 in humans. ⁶⁹	Eligibility criteria will exclude any participants who have had a previous positive SARS-CoV-2 NAAT result in Study C4591001. This will minimize the low risk of potential disease enhancement and ensure that the immune response evaluated in the study is not impacted by serological changes due to previous COVID-19 disease.	
	Study Procedures: Venipunctu	re	
There is the risk of fainting, and pain, swelling, bruising, and infection at the venipuncture site.	Venipuncture is required to collect immunogenicity data from participants.	Only qualified nurses, physicians, nurse practitioners, physician assistants, phlebotomists, or medical assistants certified or otherwise authorized to draw blood per the standards and procedures of the investigative site, as allowed by institutional, local, and country guidance, will be allowed to draw blood, to minimize local complications.	
Other			
Participants will be required to attend healthcare facilities during the global SARS-CoV-2 pandemic.	Without appropriate social distancing and PPE, there is a potential for increased exposure to SARS-CoV-2.	Pfizer will work with sites to ensure an appropriate COVID-19 prevention strategy.	

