4. STUDY DESIGN

4.1. Overall Design

This Phase 3, multicenter, randomized, double-blind study will be conducted at investigator sites in the US. The purpose of this study is to describe the safety and immunogenicity of 20vPnC and a booster dose of BNT162b2 when administered together at the same visit compared to each of the vaccines given alone in adults ≥65 years of age, as shown in Section 1.2. There are no formal comparisons and the study is not designed or powered for hypothesis testing.

Approximately 600 participants ≥65 years of age who received 2 doses of 30 µg BNT162b2 at least 6 months previously in Study C4591001 will be randomized at a 1:1:1 ratio to 1 of 3 groups with center-based randomization: Coadministration group, 20vPnC-only group, and BNT162b2-only group, stratified by prior pneumococcal vaccine status (no previous pneumococcal vaccine [naïve] or receipt of at least 1 dose of a pneumococcal vaccine [experienced]).

At Visit 1 (Day 1), participants will be assessed for eligibility, including medical history and pneumococcal vaccine history. If eligible, participants will have blood drawn for immunogenicity assessments and serological testing for prior COVID-19 infection and participants will be randomized to 1 of 3 vaccine groups. The Coadministration group (20vPnC+BNT162b2) will receive 20vPnC and a booster dose of BNT162b2, and the separate administration groups (20vPnC-only group [20vPnC+saline]) and BNT162b2-only group [BNT162b2+saline]) will receive either 20vPnC and saline or a booster dose of BNT162b2 and saline. All study interventions will be prepared and administered by an unblinded investigator site staff member. Participants will be observed for 30 minutes after vaccination by blinded investigator site staff, and any reactions occurring during that time will be recorded as AEs.

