5.2. Exclusion Criteria

Participants are excluded from the study if any of the following criteria apply:

Medical Conditions:

- 1. History of severe adverse reaction associated with a vaccine and/or severe allergic reaction (eg, anaphylaxis) to any component of the study intervention(s) or any other diphtheria toxoid—containing vaccine.
- 2. Serious chronic disorder, including metastatic malignancy, severe COPD requiring supplemental oxygen, end-stage renal disease with or without dialysis, cirrhosis of the liver, clinically unstable cardiac disease, or any other disorder that in the investigator's opinion would make the participant inappropriate for entry into the study.
- 3. History of microbiologically proven invasive disease caused by S pneumoniae.
- 4. Previous clinical or microbiological diagnosis of COVID-19.
- 5. Known or suspected immunodeficiency (aside from stable HIV meeting inclusion criterion 4) or other conditions associated with immunosuppression, including, but not limited to, immunoglobulin class/subclass deficiencies, generalized malignancy, leukemia, lymphoma, or organ or bone marrow transplant.
- 6. Bleeding diathesis or condition associated with prolonged bleeding that would, in the opinion of the investigator, contraindicate intramuscular injection.
- 7. Congenital, functional, or surgical asplenia.
- 8. Current febrile illness (body temperature ≥100.4°F [≥38.0°C]) or other acute illness within 48 hours before study intervention administration.
- 9. Other medical or psychiatric condition including recent (within the past year) or active suicidal ideation/behavior or laboratory abnormality that may increase the risk of study participation or, in the investigator's judgment, make the participant inappropriate for the study.

Prior/Concomitant Therapy:

- 10. Previous vaccination with any investigational pneumococcal vaccine, or planned receipt of any licensed or investigational pneumococcal vaccine through study participation.
- 11. Previous vaccination with any coronavirus vaccine, other than those received in Study C4591001.

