8.1. Efficacy and/or Immunogenicity Assessments

8.1.1. Immunogenicity Assessments

Blood samples (approximately 30 mL) will be collected from all participants at Visits 1 and 2 as specified in the SoA. Sample collection, processing, storage, and shipping information can be found in the ISF or equivalent manual.

Pneumococcal Responses

OPA titers for the 20vPnC serotypes will be measured in sera collected at Visits 1 and 2 from the Coadministration and 20vPnC-only groups. Participants from these 2 groups will be identified by an independent unblinded statistician;

BNT162b2 Responses

IgG levels will be measured in the SARS-CoV-2 full-length S-binding assay in sera collected at Visits 1 and 2 from the Coadministration and BNT162b2-only groups. Participants from these 2 groups will be identified by an independent unblinded statistician; additional participants from the 20vPnC-only group may be included in order to maintain the blinding of randomization assignment.

CCI

Blood samples taken at Visits 1 and 2 will also be measured for the N-binding antibody and analyzed at a central laboratory.

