9.2. Analysis Sets

For purposes of analysis, the following analysis sets are defined:

Participant Analysis Set	Description
Enrolled	All participants who have a signed ICD.
Randomized	All participants who are assigned a randomization number in the IWR system.
Evaluable immunogenicity	All eligible randomized participants who receive the study intervention(s) as assigned at Visit 1, have at least 1 valid immunogenicity result from the blood sample collected within an appropriate window approximately 1 month after vaccination (Visit 2), and have no other major protocol deviations as determined by the clinician. In the analysis for BNT162b2 immunogenicity endpoints based on the evaluable immunogenicity population, data from participants with clinically documented SARS-CoV-2 infection occurring between vaccination and 1 month after vaccination may be excluded. Participants will be grouped according to the vaccine as randomized in the analysis based on the
	evaluable immunogenicity population.
CCI	
Safety	All participants who receive at least 1 dose of the study intervention and have safety follow up after vaccination. Participants will be analyzed according to the vaccine as administered in the analysis based on the safety population.

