2.2. Study Design

This Phase 3, multicenter, randomized, double-blind study will be conducted at investigator sites in the US. The purpose of this study is to describe the safety and immunogenicity of 20vPnC and a booster dose of BNT162b2 when administered together at the same visit compared to each of the vaccines given alone in adults ≥ 65 years of age.

Approximately 600 participants ≥ 65 years of age who received 2 doses of 30 μ g BNT162b2 at least 6 months previously in Study C4591001 will be randomized at a 1:1:1 ratio to 1 of 3 groups with center-based randomization: the Coadministration group (20vPnC + BNT162b2), the 20vPnC-only group (20vPnC + saline), and the BNT162b2-only group (BNT162b2 + saline), stratified by prior pneumococcal vaccine status (no previous pneumococcal vaccine [naïve] or receipt of at least 1 dose of a pneumococcal vaccine [experienced]).

Blood will be collected at Visit 1 (prior to vaccination) and at Visit 2 (1 month after Visit 1), to assess immunogenicity. Participants will be observed for 30 minutes after vaccination and any reactions occurring during that time will be recorded as AEs.

Prompted local reactions (redness, swelling, and pain at the injection site) occurring at each injection site within 10 days after vaccination (where Day 1 is the day of vaccination) and prompted systemic events (fever, headache, chills, fatigue, muscle pain, and joint pain) and use of antipyretic/pain medications occurring within 7 days after vaccination (where Day 1 is the day of vaccination) will be collected via an e-diary after vaccination.

AEs will be collected from the signing of informed consent through Visit 2 (approximately 1 month after Visit 1). SAEs will be collected from the signing of informed consent through 6 months after Visit 1.

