4. ANALYSIS SETS (POPULATIONS FOR ANALYSIS)

Analysis populations are defined for the statistical analysis of safety and immunogenicity results in the table below. For the specified criteria in each population definition that are not associated with unblinded information (vaccination as randomized or as actually received), data for all participants will be assessed to determine if participants meet the criteria for inclusion in each analysis population prior to unblinding and releasing the database for the specified analysis, and the classifications will be documented per SOPs.

Population	Description
Enrolled	All participants who have a signed ICD.
Randomized	All participants who are assigned a randomization number in the IWR system.
Evaluable immunogenicity	All eligible randomized participants who receive the study intervention(s) as assigned at Visit 1, have at least 1 valid immunogenicity result from the blood sample collected within 20 to 49 days after vaccination(s) at Visit 1, and have no other major protocol deviations as determined by the clinician. In the analysis for BNT162b2 immunogenicity endpoints based on the evaluable immunogenicity population, data from participants with documented SARS-CoV-2 infection up to 1 month after vaccination with BNT162b2 will be excluded.

Population	Description
	Participants will be grouped according to the vaccine as randomized in the analysis based on the evaluable immunogenicity population.

CCI

Safety	All participants who receive at least 1 dose of the study intervention and have safety follow-up after vaccination. Participants will be analyzed according to the vaccine as administered in the analysis based on the safety population.
--------	--

CCI

E-diary data will be summarized among those in the safety population who report any e-diary data.

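### Must the SAP say whether a positive N-binding result, without a diagnosis, counts as documented SARS-CoV-2 infection?

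*SAP*

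**What the plan says.** SAP section 4 defines the evaluable immunogenicity population, starting from "All eligible randomized participants who receive the study intervention(s) as assigned at Visit 1", with a valid result from blood taken 20 to 49 days after vaccination and no other major deviation as judged by the clinician. For the BNT162b2 endpoints it adds that "data from participants with documented SARS-CoV-2 infection up to 1 month after vaccination with BNT162b2 will be excluded".

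Protocol section 9.2 has a narrower and softer form: "data from participants with clinically documented SARS-CoV-2 infection occurring between vaccination and 1 month after vaccination may be excluded".

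Two other provisions bear on who is affected. Exclusion criterion 4 in protocol section 5.2 bars anyone with "Previous clinical or microbiological diagnosis of COVID-19"; it does not name serology. Protocol section 8.1.1 says that "Blood samples taken at Visits 1 and 2 will also be measured for the N-binding antibody". A footnote to the schedule of activities makes vaccination independent of the test results, so a participant who is N-binding positive at Visit 1 can be enrolled and vaccinated.

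**The concern.** The SAP differs from the protocol in three ways. It drops the qualifier *clinically*, it drops the starting point of the window, and it turns *may* into *will*. A mandatory exclusion then rests on the word *documented*, which is not defined. Two analysts could build different BNT162b2 analysis sets from the same data.

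The people affected have serological evidence of infection but no diagnosis. A participant who is positive at Visit 1 falls outside the protocol's window, so the protocol clause keeps them. A participant who seroconverts by Visit 2 without illness is probably not clinically documented. Under the SAP wording either could stay or go.

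Other text seems to favour a serology rule. Protocol section 2.8.1 speaks of the need to "ensure that the immune response evaluated in the study is not impacted by serological changes due to previous COVID-19 disease", and protocol section 4.1 says that "participants will have blood drawn for immunogenicity assessments and serological testing for prior COVID-19 infection". The SAP's design summary mentions only the first purpose: "Blood will be collected at Visit 1 (prior to vaccination) and at Visit 2 (1 month after Visit 1), to assess immunogenicity".

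At stake are the per-arm geometric mean concentration (GMC) and geometric mean fold rise (GMFR) of S-binding IgG. Undiagnosed infection before Visit 1 can raise the baseline and lower the GMFR. Infection between visits can raise the Visit 2 level and be read as booster response.

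**Working it through.** **Reading the rule**

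1. *Start point.* An exclusion for infection up to 1 month after vaccination has a plain meaning: any time before that point. It needs no start date.
2. *Who is affected.* Participants with diagnosed prior COVID-19 are ineligible under criterion 4, and the evaluable set takes only eligible participants. Before Visit 1, the open start therefore matters only for serology-only positives.
3. *Authority.* Protocol section 9 and SAP section 2 let the SAP modify the protocol; an amendment is needed only for major changes to the primary endpoints. These endpoints are secondary, so the changed wording is not in itself an error.
4. *What is left.* One question remains: does an N-binding result count as documentation?

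**Size**

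The plan has no figure on this point to reproduce. Its only design calculation, protocol Table 4, reproduces (1 − 0.99^200 = 0.866) but has no bearing here.

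From the documents: 200 participants per arm (protocol section 9.5) and blood samples accepted at 20 to 49 days (SAP section 4). Assumed, because the documents give none of them: the share f with serology-only infection, the fold effect k on antibody level, the weekly infection rate, and the SD on the natural-log scale.

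If a share f has levels k times those of the rest, keeping them multiplies the arm's geometric mean by k^f. For the fold rise the factor is (post-booster fold / baseline fold)^f.

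*Infection before Visit 1, f = 1% to 5% (200 × 0.01 = 2 to 200 × 0.05 = 10 people):*

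| Baseline fold | Post-booster fold | GMFR factor at 1% | GMFR factor at 5% |
|---|---|---|---|
| 2 | 1 | 0.993 | 0.966 |
| 10 | 1 | 0.977 | 0.891 |
| 10 | 2 | 0.984 | 0.923 |
| 10 | 10 | 1 | 1 |

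*Infection between visits, 0.1% to 1% per week:* f runs from 0.1% × 20/7 = 0.29% to 1% × 49/7 = 7% (14 people).

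| Fold effect | GMC factor at 0.29% | GMC factor at 7% |
|---|---|---|
| 2 | 1.002 | 1.050 |
| 10 | 1.007 | 1.175 |

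*One arm's own 95% CI factor:* exp(1.972 × SD/√200), which is 1.087 at SD 0.6 and 1.182 at SD 1.2. The 10-fold effects at the largest shares (1/0.891 = 1.122 and 1.175) exceed the factor for the smaller SD but not for the larger. All other entries are below both.

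*Between arms:* the comparison shifts by k^(f1 − f2), which is 1 when the shares are equal. If chance gave 5% in one arm and 1% in the other, the factor would be 2^0.04 = 1.028 or 10^0.04 = 1.096.

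*Precision lost by excluding instead:* 1/√(1 − f), which is 1.005 at 1%, 1.026 at 5% and 1.037 at 7%.

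**The case for a change.** The best case for a change is that a mandatory exclusion should be reproducible from its text. The sentence is complete and points to no definition. The N-binding data will exist, and in a descriptive study the reported level is itself the result. One sentence would close the gap at no cost in data.

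Part of this stands: the evidence standard is undefined in everything that can be read. The supporting arguments are weaker.

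- The aim in protocol section 2.8.1 is attached to an entry rule on a previous positive NAAT result in Study C4591001. It is silent on serology and on exclusions at analysis.
- SAP section 2.2 is a design summary. Protocol section 8.9.2 likewise gives only immunogenicity as the purpose of the Visit 2 draw, although N-binding is measured there.
- Redactions lie where a rule could be. There is one directly before the N-binding sentence in protocol section 8.1.1. SAP sections 3.3, 3.4.2, 6.3 and 6.4 cannot be read, and SAP sections 6.2.2.1.1 and 6.2.2.2 each name a second analysis set that is blacked out. Blacked-out text cannot be treated as absent from the plan.
- Writing in an exclusion for every N-binding positive would settle more than the wording. It restricts the estimand to participants without serological evidence of infection, which the documents do not require. For Visit 2 seroconverters it also extends conditioning on an event after randomization. Reasonable statisticians would disagree on it. A companion table of all evaluable participants might repeat a redacted analysis.

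**Conclusion.** The gap is real but is one that analysts fill sensibly, so no change to the plan follows. SAP section 4 already requires population criteria that do not depend on vaccine assignment to be applied to all participants and recorded before unblinding. Infection status can be classified that way, since every participant has a Visit 1 vaccination date and samples planned at both visits. Whichever reading is adopted then applies equally to the Coadministration and BNT162b2-only groups, so no between-arm bias is expected; chance imbalance in a few infected participants remains possible.

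The effect is confined to the descriptive per-arm GMC and GMFR of S-binding IgG. SAP section 5.1 plans no hypothesis test, so no test result depends on the choice. Under the assumed inputs the GMFR would be understated by 0% to 10.9% and the GMC overstated by 0.2% to 17.5%, mostly within one arm's CI factor. Larger shares or fold effects would give larger shifts. The conclusion also rests on reading 1 month as Visit 2 and on the blinded classification being carried out as the SAP describes.

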5. GENERAL METHODOLOGY AND CONVENTIONS

5.1. Hypotheses and Decision Rules

There are no formal comparisons and the study is not designed or powered for hypothesis testing.

5.2. General Methods

Time points for local reactions and systemic events refer to data within 10 days and 7 days, respectively, after vaccination.

Prompted local reactions, prompted systemic events, and AEs will be summarized after vaccination at Visit 1, by vaccine group.

CIs for all endpoints in the statistical analysis will be presented as 2-sided at the 95% level.

5.2.1. Analyses for Binary Data

Descriptive statistics for categorical variables (eg, proportions) are the percentage (%), the numerator (n) and the denominator (N) used in the percentage calculation, and the 95% CI where applicable.

The exact 95% CI for binary endpoints for each group will be computed using the F distribution (Clopper-Pearson).¹ The 95% CI for the between-group difference for binary endpoints will be calculated using the Miettinen and Nurminen² method.

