Participants will be randomized at a 1:1:1 ratio to 1 of 3 vaccine groups. At Visit 1 (Day 1), the Coadministration group will receive 20vPnC and a booster dose of BNT162b2, the 20vPnC-only group will receive 20vPnC and saline, and the BNT162b2-only group will receive a booster dose of BNT162b2 and saline. Study intervention will be administered by

an unblinded administrator via intramuscular injection to the upper deltoid muscle of each arm.

[figure not shown]
The duration of the study for each participant is approximately 6 months.

Statistical Methods

[figure not shown]
There is no formal hypothesis test for any safety or immunogenicity results. All statistical analyses will be descriptive.

Safety will be evaluated by descriptive summary statistics (including counts and percentages of participants and the associated 2-sided 95% CIs) for local reactions at each injection site, systemic events, AEs, and SAEs for each vaccine group. With 200 vaccinated participants per group, the study will provide a greater than 86% chance of observing at least 1 AE in each group if the true rate is at least 1%.

BNT162b2 immunogenicity will be evaluated descriptively using GMCs of full-length S-binding IgG levels approximately 1 month after BNT162b2, and GMFR from before to approximately 1 month after BNT162b2, each with corresponding 2-sided 95% CIs in evaluable participants from the Coadministration and BNT162b2-only groups.

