9.3.1. General Considerations

9.3.1.1. Analysis for Binary Data

Descriptive statistics for categorical variables (eg, proportions) are the percentage (%), the numerator (n) and the denominator (N) used in the percentage calculation, and the 2-sided 95% CIs where applicable.

The exact 95% CI for binary endpoints for each group will be computed using the F distribution (Clopper-Pearson).

For the between-group difference, the 2-sided 95% CI will be calculated using the Miettinen and Nurminen method.⁷⁴

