9.3.2. Primary Endpoint(s)/Estimand(s) Analysis

Objectives	Endpoint and Estimand	Statistics & Hypothesis Test
Safety	 Proportions of participants with local reactions (redness, swelling, and pain at the injection site) within 10 days after vaccination at each injection site in each vaccine group Proportions of participants with systemic events (fever, headache, chills, fatigue, muscle pain, and joint pain) within 7 days after vaccination in each vaccine group 	Descriptive summary statistics for participants with each local reaction/systemic event within 10/7 days after vaccination by maximum severity cumulatively across severity levels
	AEs and SAEs from vaccination through approximately 1 month after vaccination	Descriptive summary statistics
	SAEs from vaccination to 6 months after vaccination	Descriptive summary statistics

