6.1.1.1.1. Main Analysis

- Estimand: The percentage of participants reporting prompted local reactions (redness, swelling, and pain at the injection site) at each injection site within 10 days after vaccination (Section 2.1).
- Analysis set: Safety population (Section 4).
- Analysis time point: Within 10 days after vaccination.
- Analysis methodology: Descriptive statistics.
- Intercurrent events and missing data: Missing values will not be imputed. CCI
- Reporting results: The count and percentage of participants with the indicated endpoint and the associated 2-sided 95% Clopper-Pearson CI for each local reaction and “any local reaction” after vaccination at each injection site in each vaccine group will be presented by maximum severity level. The denominator used in the percentage calculation will be the number of participants with any e-diary data reported after vaccination.

CCI

CCI

[figure not shown]

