6.1.1.2.1. Main Analysis

- Estimand: The percentage of participants reporting prompted systemic events (fever, headache, chills, fatigue, muscle pain, and joint pain) within 7 days after vaccination ([Section 2.1](#)).
- Analysis set: Safety population ([Section 4](#)).
- Analysis time point: Within 7 days after vaccination.
- Analysis methodology: Descriptive statistics.
- Intercurrent events and missing data: Missing values will not be imputed. CCI 
- Reporting results: The count and percentage of participants with the indicated endpoint and the associated 2-sided Clopper-Pearson 95% CI for each systemic event and “any systemic event” after vaccination in each vaccine group will be presented by maximum severity levels. The denominator used in the percentage calculation will be the number of participants with any e-diary data reported after vaccination.

CCI

CCI

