6.1.1.3.1. Main Analysis

- Estimand: The percentages of participants reporting AEs within 1 month after vaccination at Visit 1 ([Section 2.1](#)).
- Analysis set: Safety population ([Section 4](#)).
- Analysis time point: Within 1 month after vaccination.
- Analysis methodology: Descriptive statistics.
- Intercurrent events and missing data: No missing values will be imputed except for partial AE start dates ([Section 5.3](#)).
- Reporting results: The numerator (n) and the denominator (N) used in the percentage calculation, the percentage (%), and the corresponding 2-sided 95% Clopper-Pearson CI for participants reporting any AE, each SOC, and each PT within each SOC will be presented by vaccine group.

If any nonserious AEs are reported to occur before vaccination at Visit 1 or between 1 month after the last vaccination received and the 6-month follow-up (between Visit 2 and Visit 3) (outside of the protocol-specified reporting window), they will not be summarized but will be included in the AE listings.

CCI

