6.1.1.4. Serious Adverse Events

6.1.1.4.1. Main Analyses

- Estimand: The percentage of participants reporting SAEs up to 6 months after vaccination ([Section 2.1](#)).
- Analysis set: Safety population ([Section 4](#)).
- Analysis time point: Up to 6 months after vaccination.
- Analysis methodology: Descriptive statistics.
- Intercurrent events and missing data: No missing values will be imputed except for partial SAE start dates (see [Section 5.3](#)).
- Reporting results: The numerator (n) and the denominator (N) used in the percentage calculation, the percentage (%), and the corresponding 2-sided 95% Clopper-Pearson CI for participants reporting any SAEs, each SOC, and each PT within each SOC will be presented by vaccine group.

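### Is the Miettinen-Nurminen interval for between-group differences left without an endpoint or a contrast in the safety outputs?

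*SAP*

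**What the plan says.** Both documents prescribe an interval for differences in their general methods. Protocol 9.3.1.1 has "For the between-group difference, the 2-sided 95% CI will be calculated using the Miettinen and Nurminen method", and SAP 5.2.1 has "The 95% CI for the between-group difference for binary endpoints will be calculated", naming the same method. Neither names a pair of groups.

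The visible output specifications are per group:

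- Local reactions (SAP 6.1.1.1.1): "the associated 2-sided 95% Clopper-Pearson CI for each local reaction".
- Systemic events (SAP 6.1.1.2.1): "2-sided Clopper-Pearson 95% CI for each systemic event".
- AEs (SAP 6.1.1.3.1): percentages and exact intervals "for participants reporting any AE, each SOC, and each PT within each SOC will be presented by vaccine group".
- SAEs (SAP 6.1.1.4.1): the same statistics "for participants reporting any SAEs, each SOC, and each PT within each SOC will be presented by vaccine group".

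The protocol reads the same way. The synopsis promises counts, percentages and intervals "for local reactions at each injection site, systemic events, AEs, and SAEs for each vaccine group", and the table in Protocol 9.3.2 describes systemic events as proportions "within 7 days after vaccination in each vaccine group". SAP 5.1 and Protocol 4.1 say that no formal comparison is made and that the study is not powered for a test.

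**The concern.** Protocol 4.1 and SAP 2.2 give the purpose as describing coadministration relative to each vaccine alone, and Protocol 4.2 calls the two single-vaccine groups controls. A reader will therefore want the difference and its uncertainty. The visible secondary endpoints are geometric means and fold rises, so among visible endpoints only the safety outcomes could use a binary difference interval. Yet none of the four legible safety outputs mentions one.

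Two things would be at stake. The tables might show a point difference, by subtraction, with no interval, so that readers fall back on whether the per-group intervals overlap, which is stricter than the interval for the difference. Also, with three groups and two injection sites, the choice of contrasts might be made after the data are seen.

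**Working it through.** **1. The plan's own figure.** The only quantitative statement about binary safety data is Protocol Table 4. With n = 200 and P(at least 1 event) = 1 − (1 − p)^200:

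| True rate | Recomputed | Table 4 |
|---|---|---|
| 0.5% | 63.3% | 63.3% |
| 1.0% | 86.6% | 86.6% |
| 1.5% | 95.1% | 95.1% |

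It reproduces. No numerical error is involved.

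**2. Which parts of the difference interval are fixed, and where.**

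| Element | Source | Status |
|---|---|---|
| Method | Protocol 9.3.1.1, SAP 5.2.1 | fixed |
| Level and sidedness | SAP 5.2: 95%, 2-sided | fixed |
| Endpoints | SAP 5.2.1: binary endpoints, without restriction | fixed generally |
| Control groups | Protocol 4.2: each single-vaccine group is the control for its vaccine | follows from the design |
| Arm for local reactions | Protocol 6.1.1: right arm 20vPnC or saline, left arm BNT162b2 or saline | follows from the design |
| Table in which it is displayed | SAP 6.1.1 | not stated in legible text |

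The like-for-like contrasts are Coadministration against each single-vaccine group for systemic events, AEs and SAEs. For local reactions they are left arm against BNT162b2-only and right arm against 20vPnC-only. Any other local contrast would set a vaccine against saline.

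**3. What the redactions allow us to say.** Redaction marks follow the local, systemic and AE main analyses. SAP 6.3 and 6.4 do not appear. The abbreviation list includes RCDC (reverse cumulative distribution curve), which no visible section uses, so some analyses are hidden. The difference interval may be assigned in that text. Only SAP 6.1.1.4.1 (SAEs) has no mark and no difference.

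**4. Can the interval be recovered from the planned tables?** The limits are the values d that solve

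(x₁/n₁ − x₂/n₂ − d) / √V(d) = ±1.96, where V(d) = [p̃₁(1 − p̃₁)/n₁ + p̃₂(1 − p̃₂)/n₂] × N/(N − 1),

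N = n₁ + n₂, and p̃₁, p̃₂ are the maximum likelihood estimates constrained to differ by d. The only data inputs are x₁, n₁, x₂ and n₂. SAP 5.2.1 requires both numerator and denominator to be reported with each percentage.

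Worked example (assumed counts): 9/200 against 2/200, a difference of 3.5 points.

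- At d = 0.0035, p̃₁ = 0.0282 and p̃₂ = 0.0247.
- V = (0.02744 + 0.02413)/200 × 400/399 = 0.0002585, and √V = 0.01608.
- (0.0350 − 0.0035)/0.01608 = 1.96, so the lower limit is 0.35 points. The upper limit, found the same way, is 7.46 points.

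**5. Size.** The documents give no expected event rates, so the rates below are assumptions, equal in the two groups, with n = 200 each (Protocol 9.5):

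| Observed in each group | 95% interval for the difference (points) |
|---|---|
| 2/200 (1%) | ±2.68 |
| 10/200 (5%) | ±4.58 |
| 40/200 (20%) | ±7.89 |
| 100/200 (50%) | ±9.77 |

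These widths are set by the sample size. Naming a table for the interval would not alter them.

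**The case for a change.** The strongest case for a change is that a descriptive interval is not a test, so having no formal comparisons is no reason to omit it. The sponsor's own methods sections include it, and the SAE section is silent with nothing redacted. Protocol 9.3 wants the SAP final before any unblinded analysis, and naming the contrasts would serve that aim. Per-group intervals also mislead if read by overlap: in the example above they run from 2.1% to 8.4% and from 0.1% to 3.6% and overlap, while the interval for the difference excludes zero.

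Much of this stands as fact. No legible output names a difference, and the pair of groups is inferred and not written. But the overlap argument measures an error that a reader might make, and nothing in the plan invites it. The worry about choosing contrasts after seeing the data is weak, because there are only two controls and the arms are fixed. A full set of difference columns is not free either. It would give 8 local, 14 systemic, 2 AE and 2 SAE intervals, 26 in all. About 26 × 0.05 = 1.3 of them would exclude zero by chance if there were no true differences. Whether to print them is a presentation choice.

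**Conclusion.** No change to the plan is needed. What remains is a small gap in detail that the programming team will fill sensibly: the general rule says how the difference interval is computed and for what kind of endpoint, and the legible output text does not repeat it. The gap is firmly visible only for SAEs. The primary objective is to describe, its estimand is a percentage in each group, and the per-group counts with exact intervals deliver it. Following the plan as written gives no wrong or biased result.

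The conclusion rests on two readings: that SAP 5.2.1 applies to the safety endpoints as it stands, and that the tables report numerators and denominators as SAP 5.2.1 requires. If so, both the difference and its interval can be recovered, with half-widths of about 2.7 to 9.8 points at assumed equal rates of 1% to 50% and 200 per group. The effective group size will be somewhat smaller where some participants report no e-diary data. The choice of contrasts rests on the design statements in Protocol 4.2 and 6.1.1, which leave little room for another choice.
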